## 9.3 POPULATIONS FOR ANALYSES

The sample from phase I ( $n = 6$ ) will be used to refine procedures and the intervention protocol. The sample from phase II ( $n = 55$ ) will be used to analyze feasibility and acceptability data and describe pre-post changes in patient-reported outcomes.

## 9.4 STATISTICAL ANALYSES

### 9.4.1 GENERAL APPROACH

For Phase I we will use qualitative methods to analyze patient feedback from the exit interviews and descriptive statistics to summarize participants' acceptability ratings of the intervention. The interviews will be transcribed verbatim and managed in ATLAS.ti or other qualitative software for analysis. The PI and study coordinator will code interviews by domains (e.g., session relevance, delivery mode, ease of participation). Data will be analyzed using thematic content analysis to describe patient perceptions and identify patterns in the patient experience. Quantitative and qualitative findings from Phase I will be synthesized along with interventionist process notes and

included in a report. This report will be used to determine potential refinement in the recruitment procedures, intervention content, intervention delivery, fidelity forms, and retention strategies. The study team will review this report to reach consensus on refinements needed for Phase II testing.

For Phase II, we will use descriptive statistics (means, standard deviations, median, range) to examine the distribution of continuous variables. We will calculate 95% CIs for each of the feasibility measures to determine the range of estimates that are consistent with our data.

We will use one-sample negative binomial probabilities and tests of binomial proportions to compare rates of feasibility to hypothesized values. We will also summarize reasons for patient ineligibility and refusal to participate. In exploratory analyses, we will monitor and compare the patients who drop out or do not complete 3 or more sessions by demographic and clinical characteristics, and baseline scores of the measures (e.g., distress, lung cancer stigma). We will also investigate any differences in patient enrollment, retention, or adherence by treatment type (chemotherapy vs. immunotherapy) to identify an optimal patient population for a future study.

We will calculate inter-rater reliability for fidelity scores between raters of intervention fidelity.

Statistical significance will be indicated by  $p < .05$ .

---

#### 9.4.2 ANALYSIS OF THE PRIMARY ENDPOINT(S)

The primary outcome of the feasibility is enrollment ( $\geq 60\%$ ). A one-sample binomial test will be used to compare the observed enrollment percentage to 60%.

Enrollment (primary): Number of patients enrolled divided by the number of eligible patients approached

Retention: The percentage of patients who complete baseline and post-treatment questionnaires

Adherence: The percentage of patients who complete at least 3 of 5 sessions in 10 weeks.

Acceptability: Mean post-treatment patient ratings  $\geq 7/10$  on intervention satisfaction (primary), convenience, helpfulness, relevance, recommendation to others, worth doing (0 = not at all to 10 = extremely); and a brief semi-structured interview to explore factors associated with acceptability

---

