#### PRIMARY OBJECTIVES OF PHASE II

1. To determine Pathways intervention feasibility (Phase II;  $n = 55$  Pathways). Feasibility will be defined by enrollment ( $\ge 60\%$  primary feasibility outcome), retention ( $\ge 70\%$ ), adherence ( $\ge 70\%$  of patients completing 3 of 5 sessions), and mean acceptability ratings (scores of  $\ge 7$  out of 10 on intervention relevance, helpfulness, and convenience).
2. To assess preliminary data on intermediate and outcome variables and clinical utility in the single-arm pilot of Pathways (Phase II). We will assess pre (baseline) to post (~8 weeks after baseline) changes in intermediate (e.g., hope) and outcome (primary: activity and role function) variables related to a future efficacy trial. We will also describe the number of referrals to supportive services made based on the Pathways intervention.

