## 5.4 STRATEGIES FOR RECRUITMENT AND RETENTION, PARTICIPANT COMPENSATION

### **Recruitment and Enrollment.**

*Feasibility of Recruitment.* The Markey Cancer Center sees 294 newly diagnosed advanced stage lung cancer patients a year. We estimate 80% will meet performance status and brain

metastases criteria, 85% will receive required active oncologic treatments, and 10% will be excluded for already accessing palliative care or actively receiving psychological services. We estimate 179 patients per year will meet eligibility criteria. With a 50% recruitment rate (based on current estimates during COVID-19), we project recruiting 6 patients in 2 months (Phase I) and 55 patients (Phase II) in 8-9 months.

**Recruitment Strategies.** As in prior work, we will use two primary recruitment strategies: direct patient referral from oncologists and providers at the Markey Cancer Center and review of patient (per report of patients coming to clinic with diagnostic codes for metastatic lung cancer) and provider appointment schedules at the MCC. To facilitate pre-screening for eligibility, we will use the UK CCTS to have an honest broker build a report in Tableau of patients with upcoming Markey Cancer Center appointments and diagnostic codes for metastatic lung cancer. Tableau will link the CCTS Enterprise Data Warehouse data for this information and generate a report that the study team can access via a dashboard in Tableau. Tableau is a secure system that requires SSL and linkblue authentication. Additional eligibility checks may need to occur from within the UKHC medical record. Study personnel will identify upcoming oncology appointments of patients pre-screened for eligibility. Study personnel will then recruit patients in person at clinic appointments or by telephone.

We are requesting a waiver of HIPAA authorization for recruitment purposes. This waiver will allow us to review appointment schedules at the MCC to pre-screen potential patients for eligibility through the electronic health record. Patients will be pre-screened for documentation in their EHR for inclusion and exclusion criteria.

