## 9 STATISTICAL CONSIDERATIONS

## 9.1 STATISTICAL HYPOTHESES

Primary Endpoint: We hypothesize that at least 60% of eligible patients approached will enroll in the Pathways intervention in the Phase II feasibility study.

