## 9.2 SAMPLE SIZE DETERMINATION

The target sample of 6 patients for Phase I is based on the aim of refining procedures and content. We anticipate that 6 will be sufficient given that we have already had patients review proposed intervention materials to provide feedback and initial refinement.

The target sample size of 40 evaluable cases for Phase II is based on the goal of estimating the probabilities and means for 3 feasibility outcome measures (enrollment  $\geq$  60% [primary], retention  $\geq$  70%, adherence [defined as completing at least 3/5 sessions]  $\geq$  70%). We will use feasibility outcomes to inform an efficacy trial. Here we present some basic power calculations for the above 3 outcomes. Assuming a negative binomial distribution and true probability of enrollment of 60%, the probability that we would have to approach 55 or more people to recruit 40 is  $<0.05$ . If we approach  $\geq$  55 patients to enroll 40, it is unlikely the true probability of enrollment is 60% or greater, concluding a future efficacy study with our criteria may not be feasible. Out of 40 patients, if the true probability of retention is 60% we expect at least 19 patients will be retained (i.e., probability of  $n \leq 19$  retained given true retention probability of 60% is  $<0.05$ ), so if more than 21 patients are not retained, an efficacy study may not be feasible. We have 80% power (using a 2-tailed alpha of 0.05) to detect an adherence proportion of 0.72 if we assume a null hypothesis adherence proportion of 0.50.

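### Section 9.2's enrollment rule uses the wrong tail: at a true 60% rate, needing to approach 55 or more to enroll 40 has probability 0.978, not below 0.05, so the rule contradicts the ≥60% criterion

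*Combined protocol and SAP*

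**What the plan says.** Section 3 states "Feasibility will be defined by enrollment" of at least 60% as the primary feasibility outcome, and the Section 1.1 synopsis defines the primary endpoint the same way, among eligible patients approached. Section 9.1 agrees: "We hypothesize that at least 60% of eligible patients approached will enroll in the Pathways intervention in the Phase II feasibility study".

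Section 9.2 then works from 40 evaluable cases. Assuming a negative binomial distribution and a true enrollment probability of 60%, it says "the probability that we would have to approach 55 or more people to recruit 40 is" below 0.05. From a count of 55 or more it draws this conclusion: "it is unlikely the true probability of enrollment is 60% or greater, concluding a future efficacy study with our criteria may not be feasible".

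Section 9.4.2, repeated word for word in the Analysis Plan, says "A one-sample binomial test will be used to compare the observed enrollment percentage to 60" percent, and defines the rate as enrolled divided by eligible approached. Neither place gives the test's sidedness or says how its p-value bears on the criterion. Section 9.4.1 sets significance at p < .05, names both negative binomial probabilities and binomial tests, and adds: "We will calculate 95% CIs for each of the feasibility measures to determine the range of estimates that are consistent with our data". The one statement of sidedness concerns adherence: "We have 80% power (using a 2-tailed alpha of 0.05) to detect an adherence proportion of 0.72".

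Phase II is planned to enroll 55 (Sections 1.1, 4.1 and 9.3).

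**The concern.** At a true rate of 60%, enrolling 40 takes on average 40 / 0.60 = 66.7 approaches. A cutoff of 55 lies well below that average, so reaching or passing it is the expected result and cannot signal a shortfall.

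Section 9.2 is the only place where the plan turns an enrollment count into a conclusion about an efficacy trial. If it is followed, a pilot that comfortably meets the ≥60% criterion will be recorded as casting doubt on feasibility. The rule is also set for 40 enrolled, whereas the endpoint counts everyone enrolled, planned as 55.

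A smaller gap lies next to it. Section 9.4.2 tests the rate against the target value itself without saying what the result is for, so a user of the plan must work out how test, interval and criterion fit together.

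**Working it through.** **Inputs.** True rate 0.60 and 40 enrolled (9.2); 55 enrolled in Phase II (4.1, 9.3); criterion ≥60% (1.1, 3); projected recruitment rate 50% (5.4). N is the number approached until r are enrolled. This assumes independent patients with a common rate and approaching that continues until r is reached.

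**Formulas.** P(N ≥ n) = P(Bin(n − 1, p) ≤ r − 1), and P(N ≤ n) = P(Bin(n, p) ≥ r).

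**The plan's own figure (r = 40, p = 0.60).**
- P(N ≥ 55) = P(Bin(54, 0.60) ≤ 39) = 0.978. The plan states below 0.05.
- P(N ≤ 55) = P(Bin(55, 0.60) ≥ 40) = 0.035. This tail is below 0.05, so the direction appears to have been reversed.
- If 55 counted refusals rather than people approached, the probability would be 0.0002. That is below 0.05 but is not a 0.05 cutoff, and the sentence counts people approached.

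P(N ≥ 55) is still 0.69 at a true 70% and 0.11 at a true 80%.

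**Overlap with the criterion.** For 40 enrolled, the criterion is met with up to 66 approached (40/66 = 60.6%; 40/67 = 59.7%). Every count from 55 to 66, an observed 72.7% down to 60.6%, therefore meets the criterion and also triggers the 9.2 warning.

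**Correct shortfall cutoffs at p = 0.60.**
- r = 40: P(N ≥ 78) = 0.061 and P(N ≥ 79) = 0.047, so 79 or more (observed 40/79 = 50.6% or lower).
- r = 55: P(N ≥ 105) = 0.058 and P(N ≥ 106) = 0.046, so 106 or more (55/106 = 51.9% or lower).
- r = 55, exact (Clopper-Pearson) 95% CI wholly below 60%: 55/109 gives 40.7% to 60.2%, 55/110 gives 40.3% to 59.7%, so 110 or more.

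**Operating characteristics with 55 enrolled.** The criterion is met with 91 or fewer approached (55/91 = 60.4%; 55/92 = 59.8%).

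| True rate | Criterion met, N ≤ 91 | Shortfall, N ≥ 106 | Shortfall, N ≥ 110 | Not met but CI contains 60%, 92–109 |
|---|---|---|---|---|
| 50% | 0.03 | 0.65 | 0.50 | 0.47 |
| 55% | 0.17 | 0.26 | 0.15 | 0.68 |
| 60% | 0.51 | 0.046 | 0.017 | 0.47 |
| 65% | 0.85 | 0.003 | 0.001 | 0.15 |

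**The 9.4.2 test with 55 enrolled.** Using p = twice the smaller binomial tail, which agrees with the exact CI: 55/76 gives 0.034, 55/77 gives 0.0501, 55/109 gives 0.055 and 55/110 gives 0.043. The test is non-significant from 77 to 109 approached, observed 71.4% down to 50.5%. At a true 50% that happens with probability 0.50, while the criterion is met with probability 0.03.

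**The case against.** The fair defence has three parts.

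First, the criterion is already stated. Sections 1.1 and 3 make it an enrollment proportion of at least 60%, 9.4.2 gives numerator and denominator, and 9.4.1 promises a 95% CI. This stands. A reader might infer from the test against 60% that the plan treats a non-significant result as success, or that the primary endpoint has no criterion at all. The documents support neither: no section equates non-significance with success, and the one inferential use of 60%, in 9.2, looks for a shortfall. Unstated sidedness is mainly missing detail once the CI is reported.

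Second, a reader might infer that criterion, test and 9.2 rule are irreconcilable, since 40 of 55 meets the criterion, does not differ significantly from 60% (p = 0.069, twice the smaller tail) and triggers the warning. That conflict comes entirely from the wrong cutoff. With 79 in place of 55, the same data meet the criterion and trigger nothing. A point criterion and a shortfall test then simply answer different questions.

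Third, this is a Stage I single-arm pilot, and the estimate and CI will be reported in any case. That limits the damage. It does not excuse a rule whose stated error probability is below 0.05 when the true figure is 0.978, because 9.2 draws the feasibility conclusion from it.

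**Conclusion.** The enrollment rule in 9.2 is wrong and should be replaced. At a true rate of 60% it would call an efficacy study possibly infeasible about 98% of the time, and for 40 enrolled it contradicts the ≥60% criterion at every observed rate from 60.6% to 72.7%. These are exact results under 9.2's own distribution and rate.

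The point about 9.4.2 and the Analysis Plan is secondary: they should say what the test is for, because with 55 enrolled non-significance covers observed rates from 50.5% to 71.4%. The figures for 55 assume that exactly 55 are enrolled and that approaching stops there. The minimum-likelihood version of the two-sided exact test moves only the upper end, by one patient (78 rather than 77 approached).

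**What to change.** In 9.2, replace the 55-for-40 cutoff with a correct shortfall rule set for the planned 55 enrolled. Either of these fits the plan:
- one-sided 0.05, negative binomial: 106 or more approached (P = 0.046; observed 51.9% or lower);
- exact two-sided 95% CI upper limit below 60%: 110 or more approached (observed 50.0% or lower), which matches the CI in 9.4.1 and the 2-tailed level 9.2 uses for adherence.

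If 40 enrolled is kept as the basis, the one-sided negative binomial cutoff is 79 or more. Expressing the rule as a proportion or a CI limit keeps it usable if the number enrolled differs. State the operating characteristics beside it. Under the CI version, a shortfall is shown with probability 0.50 at a true 50% and 0.15 at 55%, and the criterion is met with probability 0.51 at a true 60%.

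In 9.4.2 and the Analysis Plan, add that the observed proportion, reported with its exact 95% CI, decides the ≥60% criterion; that the binomial test can only show a difference from 60%; and that non-significance does not support ≥60%. State the sidedness.

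Two choices belong to the sponsor: the one- or two-sided level, and what follows an observed rate below 60% whose CI still contains 60%. That second result is common (probability 0.47 to 0.68 at true rates of 50% to 60% under the CI version).

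The cost is wording in 9.2, 9.4.2 and the Analysis Plan, with no new data or patients. The drawback is that less favourable operating characteristics are stated openly, notably that the 50% rate projected in 5.4 ("With a 50% recruitment rate (based on current estimates during COVID-19") would be identified as a shortfall only half the time under the CI version.

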#### 9.4.3 ANALYSIS OF THE SECONDARY ENDPOINT(S)

We will describe pre-post changes in intermediate (e.g., hope) and outcome (primary: activity and role function; secondary: distress, purpose) variables using descriptive statistics. The primary goal of these analyses will be to estimate the standard deviations (SD) for use in future studies. Exploratory analyses will include intermediate variables as covariates to model the relation between outcome variables and hypothesized mediators.

We will calculate means, sd, and range of minutes per session (including preparation and documentation), interventionist post-session ratings (e.g., ease of delivering content), and mean caseload (i.e., number of patients) a week.

## 10 RISK/BENEFIT ASSESSMENT

### 10.1.1 KNOWN POTENTIAL RISKS

The proposed study poses minimal risks. Potential risks that might exist fall into three categories: (a) risks associated with the intervention; (b) risks associated with research assessments, and (c) risks associated with potential loss of confidentiality. We describe each below.

**Risks of the intervention.** The intervention asks patients to think about their personal goals, to identify actions to take towards those goals, and to identify potential barriers. For some patients, thinking about goals may cause frustration or prompt thoughts related to the ways that cancer has disrupted their lives. However, our pilot work with 60 stage IV non-small cell lung cancer patients indicates that patients can complete assessments related to their personal goals and the interference cancer has caused, identify goals that are meaningful, and view assessments of their goals and goal progress as important. As patients are asked to set goals for themselves during the week, there is a possibility that patients will not be able to meet their planned goals that week and will become distressed or discouraged as a result. We have considered this in developing our intervention protocol and identified ways to minimize risk. An additional potential risk of the intervention could be that patients may identify physical goals (i.e., activities that are physically demanding). Our pilot work suggests 10% of patients may identify a physical goal (e.g., "to start walking more").

**Risks associated with research assessments.** Research assessments include questions about depression, demoralization, lung cancer stigma, interference from cancer with personal goals, physical function, and disease-related symptoms. The instruments and methodologies are well tested and are not known to cause problems or distress on the part of the participants; however, there is the possibility that some individuals may find answering the questions distressing.

**Risks associated with potential loss of confidentiality and privacy.** There is a risk of loss of confidentiality and privacy as patients will be met in person at the Interdisciplinary Lung Clinic at Markey Cancer Center and will receive phone calls from the study coordinator.

### 10.1.2 KNOWN POTENTIAL BENEFITS

Participants may experience some benefit from feeling that they have contributed to a study that can help inform ways to help future lung cancer patients. Participants may benefit from being asked about their personal goals and monitoring their own behavior to identify areas of their lives that they want to pay more attention to for their own benefit. Participants may experience an increase in goal-directed thought and decrease in lung cancer stigma as a result of treatment. These benefits may or may not occur for any and all participants. For society as a whole, the findings will inform future intervention development and testing with lung cancer patients. Future patients may benefit from an intervention that is low burden in terms of time and cost, potentially widely available due to delivery mode, and aligned with personal values and unmet supportive care needs.

#### 10.1.3 ASSESSMENT OF POTENTIAL RISKS AND BENEFITS AND PROCEDURES TO MINIMIZE RISKS

The risk of harm or discomfort that may happen as a result of taking part in this research study is not expected to be more than in daily life or from routine physical or psychological examinations or tests. This study will determine whether a hope-enhancing intervention is feasible for advanced stage lung cancer patients in primary oncology. Results of this study will inform whether an efficacy study is warranted.

##### **Procedures to Minimize Risks.**

**Protection for risks associated with the intervention.** The biggest risk we perceive with the intervention is distress resulting from the potential of patients in the intervention to not meet their personal goals. We aim to reduce the risk of patients not meeting their goals by helping them evaluate the feasibility of goals they are setting for themselves and emphasizing small actions to help set themselves up for success. [name] (consultant) has been able to implement a hope-enhancing protocol that this intervention is based in with patients with depression where self-efficacy is low and sensitivity to perceived failure may be high. Patients will have the option of calling the study interventionist during the week if they are encountering problems with their goal. During these calls, the study interventionist will query their mood, reinforce effort and consistency in working towards meaningful activities and goals, and help problem-solve. The interventionist will help the patient set more feasible goals for the next week if needed.

As mentioned above, 10% of our sample may identify a physical health goal (e.g., to start walking more). To help minimize risk if patients identify physical goals (e.g., exercise-related or physically demanding goals), the study interventionist will communicate patient-identified goals with the oncology team, will discuss physical limitation and safety concerns related to the goal with the patient, and, if necessary, will ask the patient to wait to pursue the goal until the oncology team has cleared the activity.

**Protection for risks associated with assessment.** Patients will give voluntary responses to questions; they are told that they can decline to answer any questions that they choose. If patients express distress or frustration with the questions, study staff will remind them that these questions are voluntary and that they are meant to apply to a broad range of patients

and may not necessarily reflect each person's experience. If patients remain distressed, the study PI, [name] or other qualified member of the study team will contact them. If concerns remain, participants will be directed either to the chair of the IRB to discuss their concerns about the assessments and will be referred for psychological services at the Markey Cancer Center.

**Protection for risks associated with potential loss of confidentiality.** Prior to any contact with study participants or data, the Principal Investigator will ensure study team members have completed required institutional training in maintaining confidentiality of study data. Further, all study staff will complete training in Good Clinical Practice, which is required for clinical trial research.

Assessments completed on paper will have the participant's assigned unique ID and not the participant's name on it. Assessments completed online will be done through a secure survey site, REDCap. REDCap requires HTTPS login access. Hypertext Transfer Protocol Secure (HTTPS) is a combination of the Hypertext Transfer Protocol with the SSL/TLS protocol to provide encryption and secure identification of the server. HTTPS connections are used for payment transactions on the Internet and for sensitive transactions in corporate information systems. Assessments completed on the phone with the study coordinator will be conducted an agreed upon time by the participant when they believe they will not be interrupted. The study coordinator will complete the phone assessments from a private office. At the start of the call, the study coordinator will query whether it is a good time and whether the participant is comfortable answering questions in their current location.

Data for all participants will be kept strictly confidential, except as mandated by law. All research files will be kept on secure, password protected departmental and medical school servers. All electronic data will be stored on secure servers behind firewalls. Any paper documentation will be kept in locked file cabinets or a locked file room. Participants will be assigned a numerical code for identification in the files. Names and other identifiers will be kept in separate password protected files. Audio data will be stored on secure servers with password protected files. Study team members who are not at UK will access audio data of intervention session recordings through an FTP server. FTP divides files into segments and assigns a reference number to each segment, which are transmitted in a sequence for the receiving computer to reassemble. FTP performs automatic error detection and correction in file transfers. FTP files are considered encrypted.

All data presentation will be of aggregate-level data; patients will not be individually named.

**Psychiatric emergencies.** In the case of psychiatric emergencies, patient care will take precedence over treatment protocol. If the study coordinator or interventionist identifies concerns about a patient's mental state, the study PI or other qualified member of the study team will contact the participant and determine whether a referral to psychological counseling is needed or whether emergency services are needed. If the patient is able to continue the study, the PI or other qualified member of the study team will develop a follow-up plan using clinical judgment based upon the data and any additional information acquired through interview. This may include assessing distress prior to interventionist check-in calls or periodic telephone check-ins by the PI or other qualified member of the study team. Referrals and assistance will be given in obtaining appropriate treatment for any participant terminated from the study for safety

issues. Reports will be filed with all necessary governing bodies, including the University of Kentucky IRB and the NCI program officer.

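### The protocol treats off-site FTP access to session recordings as encrypted, but the features it cites concern file integrity, so encryption in transit is unsubstantiated

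*Combined protocol and SAP*

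**What the plan says.** The relevant text is the paragraph of protocol section 10.1.3 on protection against loss of confidentiality. On storage it says: "Audio data will be stored on secure servers with password protected files". On access from outside it says: "Study team members who are not at UK will access audio data of intervention session recordings through an FTP server". It then describes the transfer method: "FTP divides files into segments and assigns a reference number to each segment", with the receiving computer putting the parts back together, and "FTP performs automatic error detection and correction in file transfers". It ends: "FTP files are considered encrypted".

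Earlier in the same paragraph, web access to REDCap is described as HTTPS, which adds SSL/TLS "to provide encryption and secure identification of the server".

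Section 10.1.1 lists "risks associated with potential loss of confidentiality" as one of three categories of risk to patients. Section 6.2.1 has every intervention session audiorecorded and reviewed for fidelity under stated sampling rules. The separate Analysis Plan does not address the handling of recordings.

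**The concern.** The encryption sentence reads as the conclusion of the two sentences before it, and it does not follow from them. Segmentation and error correction keep a file complete and uncorrupted. Neither prevents someone who intercepts the file from listening to it.

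The material is sensitive. In the sessions, patients with advanced lung cancer talk about values, family, symptoms, stigma and self-blame (section 6.1.1 and Table 1). A study number on the file does not disguise a voice. Section 8.1 has exit-interview transcripts deidentified, but the text available to this review states no such step for session audio.

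The wording also has consequences beyond the protocol. Section 11.1.1.2 says that consent will explain how session data are kept confidential. An assurance of encryption without a stated basis could be passed on to patients and to the IRB.

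**Working it through.** The plan gives no figure to reproduce. The check is a comparison of texts, followed by a bound on the number of recordings.

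**Does the stated basis support the claim?**

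| Route | Stated basis for security | Encryption mechanism named? |
|---|---|---|
| REDCap (section 10.1.3) | HTTPS, with SSL/TLS as the source of encryption | Yes |
| Tableau pre-screening report (section 5.4) | SSL and institutional log-in | Yes |
| Sessions by Zoom (section 11.1.2) | HIPAA-compliant institutional account | No, but a compliance standard is named |
| Off-site access to session audio (section 10.1.3) | Numbered segments; error detection and correction | No |

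For the last route no secured variant, key or file-level encryption is named.

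**Can the REDCap protection be carried over?** No. Section 11.1.5.1 leaves audio files and transcripts out of the data held in REDCap or Excel, so the HTTPS description does not reach them.

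**Do the other stated safeguards cover transfer?**
- Secure servers, firewalls and password-protected files (section 10.1.3) are described for storage. The text does not say whether a password stays with a file while it is sent.
- Pausing the recording at the patient's request, or when medical staff approach (sections 11.1.1.2 and 11.1.2), limits what is recorded, not how the recording travels.

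**How many recordings could be involved?** Inputs: 6 Phase I and 55 Phase II patients, five sessions each (section 4.1). Section 6.2.1 requires review of all Phase I sessions, all sessions of the first 10 Phase II patients, and 10% of the remaining sessions.
- Recorded at full attendance: 6 × 5 = 30 in Phase I and 55 × 5 = 275 in Phase II; 30 + 275 = 305.
- Reviewed in Phase I: 30.
- Reviewed for the first 10 Phase II patients: 10 × 5 = 50.
- Remaining Phase II sessions: (55 − 10) × 5 = 225; 10% of 225 = 22.5.
- Reviewed for fidelity in total: 30 + 50 + 22.5 = 102.5, or about 102.

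This is a ceiling on fidelity review, because it assumes that everyone completes all five sessions. The adherence target is only that at least 70% of patients complete 3 of 5. The protocol does not say how many raters work off-site, so the number of files sent could be anywhere from none to that ceiling for fidelity review. Recordings are also used to rate enactment (section 6.4) and to monitor adverse events (section 10.2.2). No sampling fraction is given for those uses, so they are not counted here.

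**The case against.** A reader might infer that the recordings travel unencrypted. The documents do not show this. They name an FTP server but not its configuration, and a secured setup may be in place. What they show is an assurance without a stated mechanism.

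A reader might also infer that this sentence is the only protection for the audio, or that the trial's risk assessment depends on it. Neither is supported. The storage and content safeguards are real, and section 10.1.3 adds numerical codes, separately held identifiers and staff training. Section 10.1.1 attributes the confidentiality risk to meeting patients in clinic and telephoning them, without mentioning recordings. The minimal-risk statement that opens section 10.1.3 does not cite FTP. Nor are the recordings the most identifying data in the study: the master list of names and record numbers (sections 8.1 and 11.1.2) is more so, and nothing routes that list through FTP.

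The text available to this review also has gaps. Section 11.1.2 promises confidentiality procedures by study stage; the pages after its paragraph on patient interactions were not available, and neither were the consent forms. Further safeguards for audio may be stated there, and the consent wording may need no change.

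All of this stands, and it limits the point. It does not rescue the sentence, which would still rest on features that are not encryption and would need to agree with any safeguard stated elsewhere. It is also fair to say that no endpoint, sample size or analysis is touched. The point concerns the protection of patients' data.

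**Conclusion.** The concern holds in a limited form. Section 10.1.3 supports its encryption statement with features that protect integrity, and it names no encryption mechanism for off-site access to session audio. Encryption in transit is unsubstantiated; its absence is not established.

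At most about 102 recordings would be reviewed for fidelity, assuming full attendance and the sampling rules of section 6.2.1; the off-site share is unknown. The conclusion rests on the available text and on the premise that a patient can be recognised by voice.

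The change should be made, because the section offers this text as mitigation of one of the three named patient risks and the correction is small.

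**What to change.** In section 10.1.3:
1. Delete the sentence "FTP files are considered encrypted", or replace it with the transfer method actually used and how that method encrypts the files.
2. Require that off-site staff reach session audio only through a channel with a named encryption mechanism, for example SFTP, FTPS or an encrypted institutional file share.
3. Say whether the password protection described for stored audio stays with a file during transfer.

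Then check that the consent description of how session data are protected agrees with the corrected text, and amend it only if it does not.

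The cost is a short protocol edit and, if the present server does not already qualify, a minor server or account setup. There is no effect on data or analysis.
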